9.2.3.1 Reference Groups

Given the inherent difficulties in identifying a comparison group (Covington, 2009), several different methods may be used to review the data for safety signals. As described below, background rates from external surveillance sources and rates from published literature will be the primary comparators. To the extent possible, comparator rates will be age-adjusted to reflect the age distribution of the Menveo Pregnancy Registry population.

Background Rates on Pregnancy Outcomes

Background rates in the general population on pregnancy outcomes, such as premature birth and LBW, are readily available from national vital statistics or publications in the scientific literature (Martin, 2012).

Background Rates on Congenital Anomalies

Published rates of MCMs are available from the Centers for Disease Control and Prevention (CDC)'s Metropolitan Atlanta Congenital Defects Program (MACDP), which is an ongoing population-based birth defects surveillance program (Correa, 2007). The primary objectives of MACDP are to regularly and systematically monitor births of malformed infants for changes in incidence or other unusual patterns suggesting environmental influences, and to develop a case registry for use in epidemiological studies. MACDP actively searches for MCMs among the 50,000 annual births to residents of metropolitan Atlanta's 5 counties and abstracts medical records at all Atlanta obstetric hospitals, Atlanta pediatric referral hospitals, genetics labs, and vital records (Correa-Villasenor, 2003). While there are inherent problems with comparing data from women exposed to specific vaccines in pregnancy with background rates from the general population, this is not an unrealistic comparison (Honein, 1999), and background rates may be the only practical comparator. MACDP has been used as a comparator by over 60% of pregnancy registries identified in a recent survey (Covington, 2009). When an analysis includes data from an external comparator, it is important to thoroughly

understand the methodology of the external comparator, and to take this into consideration when designing the analysis plan ([Kennedy, 2004](#)).

Background Rates from Literature or Other Studies

The registry is committed to identifying other appropriate comparison groups, and research of the literature and other sources, such as other pregnancy registries or observational studies, will continue in order to obtain appropriate background rates.

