9.3.3 Other Variables

Maternal characteristics: Age, ethnicity, race

Prenatal data: Last menstrual period (LMP), estimated date of delivery (EDD), corrected estimated date of delivery (CEDD)

Prenatal tests: Name of test, date of test, result

Obstetrical history: Previous pregnancies, live births, stillbirths, SABs, induced abortions (IABs), births with congenital malformations, family history of congenital malformations

Concomitant medical conditions

Concomitant medications and vaccines

Alcohol, tobacco, and illicit drug use

Pregnancy outcomes

Each pregnancy outcome will be classified in 1 of the following mutually exclusive categories:

- Live birth: an infant born alive
- Stillbirth: a fetal death occurring at 20 weeks' gestation or greater, or if gestational age is unknown, a fetus weighing 500 g or more
- SAB: fetal death or expulsion of products of conception prior to 20 weeks' gestation. Terminology may include missed abortion, incomplete abortion, and inevitable abortion.
- IAB: voluntary interruption of pregnancy, including pregnancy termination that occurs electively, to preserve maternal health, or due to fetal abnormalities

- Ectopic pregnancy: implantation of a conception outside of the uterus
- Molar pregnancy: a conception that results in a gestational trophoblastic tumor

Infant Outcomes: Gestational age, birth weight, sex

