The expected low frequency of Menveo exposure in pregnancy will limit the statistical power of this study. As noted below, there should be sufficient power to identify risks for relatively common outcomes such as preterm birth and LBW. However, there is less power to identify risks of rarer outcomes such as MCM.

According to the CDC MACDP, the prevalence rate of MCMs for mothers <25 years of age in the US is 2.54% ([Correa, 2007](#)). With a sample size of 58 first trimester exposed pregnancies resulting in a live birth, the study will have 80% power to detect a 4.46-fold increase in the prevalence rate of MCMs as compared with the CDC MACDP rate.

According to the CDC National Vital Statistics System (NVSS), the prevalence rate of preterm birth for mothers <25 years of age is 12.37% ([Martin, 2012](#)). With a sample size of approximately 58 exposed live births, the study will provide 80% power to detect a statistically significant 1.99-fold increase in the prevalence rate of preterm birth as compared with the CDC NVSS rate.

According to the CDC NVSS, the prevalence rate of LBW for mothers <25 years of age is 8.70% ([Martin, 2012](#)). With a sample size of 58 exposed live births, the study will provide 80% power to detect a statistically significant 2.40-fold increase in the prevalence rate of LBW as compared with the CDC NVSS rate.

The registry acknowledges the challenges of enrolling this number of exposed pregnancies and will carefully monitor enrollment trends and outcomes. This is an open registry with initiation of patient recruitment from the time of launch.

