9.6.2 Software and Hardware

Power calculations presented in this protocol were conducted using SAS statistical software and a 1-sample binomial distribution with a 1-sided Type I error rate of 5%. Data analyses will be performed similarly using SAS (version 9.2 or higher; SAS Institute, Cary, NC).

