Invalid registry reports and pregnancies deemed lost to follow-up will be excluded from the primary analysis. Retrospective reports will not be included, although retrospective cases with MCMs will be reviewed and reported separately for signal detection purposes.

Sequential Pregnancies

The number and outcome of sequential pregnancies will be noted and presented. Sequential pregnancies will be included in the analytic dataset.

Multiple Gestation Pregnancies

The number, type (e.g., twin, triplet), and outcome of multiple gestation pregnancies will be noted and presented. Multiple gestation pregnancies will be included in the analytic dataset.

General Considerations for Data Analyses

This study is observational, and epidemiological methods will be employed for data collection and analyses.

Descriptive analysis will be performed for all prospective, evaluable data. The summary statistics for continuous and categorical variables to be used will be specified in the statistical analysis plan (SAP) but may include means, standard deviations, medians, minimums, maximums, percentiles, n's, and percentages. Adjustment for confounders of potential associations will be made with multivariate regression methods if appropriate and will be described in detail in the SAP.

The registry will identify the number of cases for the primary outcomes of MCM, preterm birth, LBW, and in addition for second trimester SABs; proportions of these outcomes will be calculated with 1-sided 95% confidence intervals from the total number of pregnant women or live births, or in the case of second trimester SABs, the subset of women exposed prior to the 20th week of gestation.

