9.7.3 Statistical Methods

Overall and stratum-specific point estimates and 1-sided 95% confidence intervals will be calculated using the exact binomial distribution for prevalence rates of MCMs, preterm birth, and LBW among pregnant women exposed to Menveo and their live births. Most structural defects have their origins in the first trimester of pregnancy, the period of organogenesis. In addition to overall prevalence of MCM, the analysis of MCMs will be stratified by trimester of exposure to Menveo. The prevalence rate of combined MCMs reported to the registry will be calculated as a proportion with the number of MCMs as the numerator and the number of live births as the denominator, among women with first trimester exposure. Pregnancy losses with reported MCMs occurring at or after 20 weeks' gestation will be included in the numerator of the estimate of risk for MCMs to increase sensitivity and to allow comparison of outcomes with the CDC MACDP, which calculates rates by this convention. A secondary analysis will be conducted including pregnancy losses with reported MCMs occurring at less than 20 weeks' gestation in the calculation of risk. The prevalence rate of combined MCMs in exposed cases will be compared with that of the CDC MACDP ([Correa, 2007](#)).

Only cases meeting the CDC MACDP criteria for a defect or with 2 or more conditional defects will be included in the primary analysis. Single minor defects do not constitute a MCM according to the CDC MACDP classification; therefore, they will be listed in the report, but not included in the primary analysis.

The prevalence rate of preterm births and LBW will be calculated as proportions, with the number of live births as the denominator. These prevalence rates in exposed cases will be compared with those of the CDC NVSS ([Martin, 2012](#)). Because MCMs are often associated with preterm birth and LBW, infants with MCMs will be excluded from

analyses of these outcomes and will not be counted in the numerator or denominator when prevalence rates are determined.

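### Preterm birth and LBW rates count each infant of a multiple pregnancy as an independent live birth, and the comparator is not aligned for plurality; the effect is modest and cheap to remove

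*Protocol*

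**What the plan says.** Under Multiple Gestation Pregnancies, Section 9.7 of the protocol says "Multiple gestation pregnancies will be included in the analytic dataset"; their number, type and outcome are also to be presented. Section 9.3.3 defines a live birth at the level of the infant. Section 9.7.3 then fixes the rate and the interval: "The prevalence rate of preterm births and LBW will be calculated as proportions, with the number of live births as the denominator", and "Overall and stratum-specific point estimates and 1-sided 95% confidence intervals will be calculated using the exact binomial distribution".

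On the comparator, Section 9.2.3.1 says that, as far as possible, "comparator rates will be age-adjusted to reflect the age distribution of the Menveo Pregnancy Registry population". No other characteristic is named for alignment. Section 9.7.3 names the national vital statistics as the reference for both outcomes and does not say whether those rates include multiples.

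Section 9.7.3 removes infants with major malformations from both numerator and denominator of these two rates, because malformations tend to go with early delivery and low weight. It has no such step for multiples.

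The planning figures in Section 9.5 use the same unit: "With a sample size of approximately 58 exposed live births, the study will provide 80% power to detect a statistically significant 1.99-fold increase" in preterm birth. Section 9.6.2 gives the method as "a 1-sample binomial distribution with a 1-sided Type I error rate of 5" per cent.

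**The concern.** An exact binomial limit treats every infant as a separate independent trial. Co-twins are delivered together, so in practice both are preterm or neither is, and their birth weights are related. Plurality is also a strong risk factor for both outcomes, yet it is neither restricted nor matched to the reference.

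Preterm birth and LBW are two of the three primary outcomes, with about 7 and 5 expected events. At such counts, the number of twin pairs that happen to enrol, which has nothing to do with the vaccine, can change whether an excess appears. It works in both directions: a registry without twins, set against a rate that includes them, is conservative and could miss an excess.

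**Working it through.** **Inputs from the protocol.** n = 58 live births; reference rates 12.37% (preterm) and 8.70% (LBW); one-sided 5%; one-sample exact binomial (Sections 9.5 and 9.6.2).

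**Step 1: the protocol's own figures.** Take the smallest count r with P(X ≥ r | n = 58, p0) ≤ 0.05.

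| Outcome | Expected events | r | Attained size | Power at stated ratio |
|---|---|---|---|---|
| Preterm | 58 × 0.1237 = 7.2 | 12 | 4.94% | 79.9% at 1.99-fold |
| LBW | 58 × 0.0870 = 5.0 | 10 | 2.70% | 79.8% at 2.40-fold |

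The stated detectable ratios reproduce, with 58 infants taken as independent. The thresholds of 12 and 10 are inferred from this calculation; the protocol fixes no signal rule.

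**Step 2: double counting alone.** Give twins the reference rate, make each pair fully concordant, and convolve Bin(58 − 2j, p0) with j pairs.

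| Pairs j | Preterm false-signal rate | LBW false-signal rate |
|---|---|---|
| 0 | 4.9% | 2.7% |
| 1 | 5.2% | 2.9% |
| 2 | 5.5% | 3.2% |

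This adds about 0.3 percentage points per pair for preterm birth and slightly less for LBW.

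**Step 3: add higher risk in twins.** These assumptions are not in the document: twins are a share t = 2-4% of live births; a proportion pt = 40-60% of twins are affected; within-pair correlation ρ is 1 for preterm birth and 0.5 for LBW; the reference rate includes multiples. The formulas are:

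- singleton rate ps = (p0 − t·pt)/(1 − t)
- P(both affected) = pt² + ρ·pt(1 − pt)
- P(exactly one affected) = 2[pt − P(both affected)]
- number of pairs j ~ Bin(29, t)

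At t = 3% and pt = 50%:

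- preterm ps = (0.1237 − 0.015)/0.97 = 11.2%
- LBW ps = (0.0870 − 0.015)/0.97 = 7.4%
- P(j = 0) = 0.97^29 = 41%; P(j = 1) = 29 × 0.03 × 0.97^28 = 37%; P(j = 2) = 16%

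| Pairs j | Probability | Preterm false-signal rate | LBW false-signal rate |
|---|---|---|---|
| 0 | 41% | 2.6% | 1.0% |
| 1 | 37% | 5.6% | 2.8% |
| 2 | 16% | 10.5% | 6.8% |

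Averaged over the chance number of pairs, across t = 2-4% and pt = 40-60%, the rate is 5.4-6.4% for preterm birth (4.9% under independence) and 3.1-4.0% for LBW (2.7% under independence).

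**Step 4: can pairs produce a signal alone?** Two fully affected pairs supply 4 infants. That leaves 12 − 4 = 8 preterm or 10 − 4 = 6 LBW infants to come from the rest; with one pair it is 10 or 8. If the remaining infants are at the reference rate, the chance of reaching the threshold is 15% (preterm) and 11% (LBW) with one fully affected pair, and 35% and 33% with two.

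**The case against.** Several counter-arguments have force.

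- **The independence violation is small.** Step 2 shows about 0.3 points per pair. The larger swings come from case mix: twins are assumed to be at higher risk, and conditioning on the realised number of any strong risk factor gives a similar spread. This stands.
- **Inclusion may be like for like.** If the national rates cover all live births, keeping multiples matches them. This stands as far as it goes, but the protocol does not say what the rates cover, and with one or two pairs expected the registry's plurality can differ sharply from the reference by chance.
- **A twin-driven excess would be visible.** Section 9.7 presents multiples, and Section 12.2 lists multiple birth and preterm delivery in the annual updates. True, but visibility corrects neither the interval nor the comparator.
- **The registry describes rather than tests, and the SAP may add detail.** Section 9.7.1 disclaims hypothesis tests, and Section 9.7.3 leaves an open list of confounders to the SAP. However, inclusion, unit and interval method are fixed in the protocol, Section 9.9 relies on confidence intervals to judge chance, and Section 9.5 claims statistically significant detectable increases.
- **The twin inputs are assumed.** Nothing in the protocol gives a twin share for a mainly adolescent population. This stands, and is why ranges are shown.

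A reader might also infer that Section 9.3.3 cannot be applied to discordant twins, since it says "Each pregnancy outcome will be classified in 1 of the following mutually exclusive categories". The document does not support that: the categories are worded by infant or fetus, and Section 10.0 assigns infant identifiers. At most a clarification is due.

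**Conclusion.** The point holds in limited form. The protocol counts each infant of a multiple pregnancy as an independent live birth for two primary outcomes, aligns the comparator for age only, and does not say whether the reference rates include multiples. It already removes malformed infants from these rates for an analogous reason.

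Under the assumptions of Step 3, the average false-signal rate rises by about 0.5 to 1.5 points for preterm birth (5.4 − 4.9 to 6.4 − 4.9) and by 0.4 to 1.3 points for LBW (3.1 − 2.7 to 4.0 − 2.7). If the reference rates are for singletons only, the bias would be larger.

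Two stronger readings are tempting and not supported. One is that the one-sided 5% error breaks down: LBW stays below 5% on average and preterm birth exceeds it only slightly. The other is that a twin pair or two creates a false signal: they can tip a borderline count, but 6 to 10 further affected infants are needed. The 10.5% and 6.8% figures apply only given exactly two pairs, about a 16% event at 3% twins. The power figures in Section 9.5 are not in error on their own terms.

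**What to change.** In Sections 9.7 and 9.7.3:

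1. Report preterm birth and LBW in singleton live births against age-adjusted singleton rates from the same national source, if available. Make this the primary comparison, or at minimum a pre-specified sensitivity analysis.
2. State whether the reference rates of 12.37% and 8.70% include multiples.
3. For any all-births rate, take the pregnancy as the unit or use an interval that allows for clustering within pregnancy.
4. Optionally, clarify in Section 9.3.3 that outcome is classified per fetus.

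Plurality is already collected, so the work is wording and one comparator table. At 2-4% twins, 58 × 0.02 = 1.2 to 58 × 0.04 = 2.3 infants would leave the singleton rates, so about 1-2.

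If singletons become primary, the reference rates and detectable ratios in Section 9.5 must be restated. As an illustration, assume 3% twins with 60% preterm and 57% LBW, which gives singleton rates of 10.9% and 7.2%. With 56-57 singletons, the ratios detectable with 80% power become 2.13-2.16 for preterm birth (stated: 1.99) and 2.46-2.69 for LBW (stated: 2.40). A sensitivity analysis alone avoids that restatement.

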8.0 RESEARCH QUESTION AND OBJECTIVES

The objective of the Menveo Pregnancy Registry is to evaluate pregnancy outcomes among women immunized with the Menveo vaccine within 28 days prior to conception or at any time during pregnancy. The primary outcomes of interest include major congenital malformations (MCM), preterm birth, and low birth weight (LBW).

Other pregnancy outcomes will be collected, including stillbirths and SABs. The probability of SAB varies greatly as a function of when the pregnancy is enrolled in the registry ([Savitz, 2002](#)). Because pregnancies will be reported to the registry at different and imprecise times during gestation, calculation of the prevalence rate of SAB from the registry is deemed inappropriate and could lead to erroneous conclusions. For example, if a woman enrolls in the registry at 16 weeks of pregnancy, only an SAB after this time could be detected and included in prospective reports. Similarly, SABs occurring earlier in gestation may not have been recognized and/or reported.

This registry is primarily descriptive and designed to detect potential safety signals rather than test hypotheses.

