9.2 Setting

9.2.1 Study Period

The pregnancy registry will be implemented after approval by applicable regulatory authority and central institutional review board (IRB). The target enrollment goal of the registry is 100 prospectively enrolled pregnant women. The data collection process for each participant will begin at enrollment (during pregnancy), and follow-up will occur at the end of the second trimester (approximately 24 weeks' gestation) and at pregnancy outcome (delivery or early termination).

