9.2.3 Study Population Selection

The minimum criteria required for enrollment into the registry are as follows:

- Sufficient evidence to confirm that Menveo exposure occurred within 28 days prior to conception or at any time during pregnancy

- Sufficient information to determine whether the pregnancy is prospectively or retrospectively registered (ie, whether the outcome of pregnancy was known at the time of first contact with the registry)
- Date the pregnancy exposure is registered
- Full reporter (ie, HCP) contact information to allow for follow-up (name, address, etc.)

Because registry enrollment is open to all eligible pregnant women, an active recruitment campaign will reach out to immunization providers and their patients in a broad variety of settings. The recruitment strategy will target HCPs who are known to immunize patients specifically with the Menvo vaccine. These providers will be identified through NVD Menvo distribution data and medical science liaisons (MSLs), as well as HCP provider networks and health maintenance organizations (HMOs).

This targeted awareness will include the distribution of a comprehensive informational kit designed to solicit interest among pregnant women in registry participation. All messaging will be in line with product labeling.

The kit may include:

- Branded registry information sheet and/or brochure that will briefly describe the registry purpose and procedures
- Enrollment form and sample patient consent form
- Prescribing information
- Participant consent to contact card (this card enables the RCC to contact the potential patient and provide additional information about the registry)

Persistent awareness activities incorporating the above awareness materials as well as a variety of other approaches such as internet, product labeling, and messaging by MSLs may also be used, including the following:

- Internet:
 - FDA listing of pregnancy registries on www.fda.gov
 - www.clinicaltrials.gov
 - Society for Maternal-Fetal Medicine listing of registries
 - PPD website
 - NVD website
- Print:
 - Menvo prescribing information

- Menveo medication guide
- Medical journal advertising and/or direct to physician advertising
- Registry contact information in report(s)
- Education:
 - MSL outreach to treating HCPs
 - Scientific presentations and publications
 - Distribution of report(s) to HCPs

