9.4.1 Operational Exposure Definition

Menveo administered 28 days prior to conception or at any time during pregnancy (from conception until pregnancy outcome) will constitute exposure. The 28-day window prior to conception corresponds with the time to immunologic response as indicated in the Menveo product label (Menveo package insert, 2012). Menveo exposure will be further categorized by earliest trimester of exposure. Menveo is not indicated in pregnancy and is typically given to adolescents and young adults. Thus, the vast majority of pregnancy exposures will be inadvertent first trimester exposures, most likely prior to recognition of the pregnancy. For this registry, gestational weeks will be estimated from the most

reliable EDD as reported by the HCP. If a CEDD is provided by the HCP, it will be used instead. The date of conception will be calculated as the most reliable EDD minus 38 weeks. If the EDD is not available or never estimated, the first day of the LMP may be used to estimate gestational age. The second trimester will be considered to begin at week 14 after the date of conception or LMP, and the third trimester, at week 28. If there is a discrepancy between gestational age calculated from LMP and reported gestational age, the HCP will be asked to verify the data.

When a pregnant woman enrolls in the registry, she will be asked when and where she was immunized with the Menveo vaccine. She will then be asked to provide a medical release that allows the registry to confirm Menveo vaccination with the appropriate source. The registry will contact the Menveo vaccination provider to confirm the vaccination date, brand, and lot number. If HCPs provide de-identified data to the registry, they must be able to verify the Menveo vaccination and date of vaccination.

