9.5 Study Size

Currently the market share of Menveo is approximately 20%, with an annual absolute dose distribution of 1.8 million in 2012. It can be assumed that market shares will remain stable over the course of the 3-year duration of the study. The Advisory Committee on Immunization Practices (ACIP) recommends routine administration of a MenACWY vaccine for all persons aged 11 through 18 years. A single dose of vaccine should be administered at age 11 or 12 years, and a booster dose should be administered at age 16 years. It is roughly estimated that of all Menveo vaccinations, approximately 76% are provided to individuals less than 18 years of age ([Novartis Vaccines and Diagnostics, 2012](#)). Given the low rate of pregnancy in this age group, exposure during pregnancy at the recommended ages can be expected to occur infrequently. Likewise, vaccination among women of peak reproductive age (25-29 years) can also be expected to be rare ([Ventura, 2012](#)). In addition, willingness to participate and completion of follow-up in the pregnant adolescent population are expected to be very low. It is therefore anticipated that, per year, approximately 15 exposed women will be enrolled through the registry system and that approximately 60 supplemental identified exposures of Menveo in pregnancy can be expected from external sources.

The registry is expected to prospectively enroll approximately 100 women with exposure to Menveo 28 days prior to conception or during pregnancy over a 3-year period. Approximately 58% of these pregnancies can be expected to result in a live birth ([Ventura, 2012](#)). Given the patient population will be mainly adolescents, a high percentage of these pregnancies can be expected to be unintended, unwanted, and likely

to result in IAB. Therefore, it is anticipated that the registry will yield approximately 58 live births. It is expected that the vast majority (99%) of pregnancy exposures will occur within 28 days prior to conception or early in the first trimester (before pregnancy status is known). If exposures occur later in pregnancy, results will be stratified by trimester of exposure, acknowledging that the power of stratified analyses to detect statistically significant differences will be limited by the sample size of each subgroup.

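### The second-trimester SAB proportion is limited by time of exposure, not time of enrolment, so its denominator includes women who could not be observed as cases

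*Protocol*

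**What the plan says.** All references are to the protocol.

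- **The estimate.** Section 9.7 (General Considerations for Data Analyses) adds second-trimester SAB to the three primary outcomes as a proportion with a 1-sided 95% interval. The denominator is "or in the case of second trimester SABs, the subset of women exposed prior to the 20th week of gestation".
- **The stated objection to SAB rates.** Section 8.0 says that "calculation of the prevalence rate of SAB from the registry is deemed inappropriate and could lead to erroneous conclusions", because women are reported at differing and imprecise gestational ages. Its example is that "if a woman enrolls in the registry at 16 weeks of pregnancy, only an SAB after this time could be detected". It adds that early losses may go unrecognised or unreported.
- **The window.** Section 9.3.3 defines SAB as "fetal death or expulsion of products of conception prior to 20 weeks" of gestation. Section 9.4.1 states: "The second trimester will be considered to begin at week 14 after the date of conception or LMP".
- **Who is counted.** Data collection on a participant starts at enrolment (9.2.1). Prospective registration is open until the outcome is known. Reports made after the outcome are retrospective and stay out of the risk calculation (9.7). Networks and HMOs that report every exposed pregnancy count as prospective (9.7).
- **Exposure timing.** Section 9.5 expects that the "vast majority (99%) of pregnancy exposures will occur within 28 days prior to conception or early in the first trimester".

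**The concern.** A restriction on exposure before week 20 looks like an at-risk restriction, but it does not act as one. With 99% of exposures expected around conception or early in the first trimester, it removes almost nobody. What decides whether a second-trimester loss can be seen in an individually enrolled woman is when she enrols, and the denominator ignores that.

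This is the only SAB proportion the protocol plans. Section 7.0 records seven SABs in the pre-licensure studies, all among MenACWY recipients (37 of the 43 pregnancies), so readers will look for this figure. If it is read as the risk of loss among women followed through the second trimester, it errs toward reassurance by an amount that depends on when women happened to enrol.

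**Working it through.** The protocol gives no figure for second-trimester SAB, so there is none to reproduce. The power figures in 9.5 concern other outcomes and are not affected.

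**Step 1: who can be a case.** A case is a loss between the start of the second trimester and week 20.

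| Report | In denominator | Can be a case |
|---|---|---|
| Individual, enrolled before the second trimester, still ongoing at its start | yes | yes, whole window |
| Individual, enrolled between that start and week 20 | yes | part of the window |
| Individual, enrolled at week 20 or later | yes | no, apart from a missed abortion recognised late |
| Complete-capture network/HMO, ongoing at that start | yes | yes, whole window |
| Any route, ended before that start | yes | no |

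**Step 2: part-window observation.** Dated from LMP, the window is 20 − 14 = 6 weeks. Section 9.4.1 sets conception at EDD minus 38 weeks, which is LMP + 2 weeks if EDD is LMP + 40 weeks (assumed). Dated from conception, the window then opens at LMP week 16 and lasts 20 − 16 = 4 weeks.
- Enrolment at LMP week 16 (Section 8.0's example): 4/6 of the window is seen under LMP dating, all of it under conception dating.
- Enrolment at LMP week 17: 3/6 = 0.50 or 3/4 = 0.75.

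**Step 3: size against pregnancies ongoing and observable.** Let s be the share of reports enrolled individually, q the share of those joining at week 20 or later, and e the share of all reports that ended before the second trimester. If everyone else has the same risk and is seen for the whole window,

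planned proportion ÷ at-risk proportion = 1 − s·q − e.

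Section 9.5 expects about 15 individual enrollees per year and about 60 exposures from external sources, without making clear whether the 60 is per year or in total. Read per year, s = 15/75 = 20%. Read as a total, s = 45/105 = 43%, which fits the target of 100 better: 15 × 3 + 60 = 105, against (15 + 60) × 3 = 225. Both readings assume the external sources are complete-capture networks, which 9.5 does not say; s = 100% is the extreme. The values of q and e are assumptions.

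| | s = 20% | s = 43% | s = 100% |
|---|---|---|---|
| q = 10%, e = 0 | 0.98 | 0.96 | 0.90 |
| q = 25%, e = 0 | 0.95 | 0.89 | 0.75 |
| q = 50%, e = 0 | 0.90 | 0.79 | 0.50 |
| q = 50%, e = 10% | 0.80 | 0.69 | 0.40 |

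The factor is 1 if nobody joins after the second trimester starts and no pregnancy ended before it. The 58% live births expected in 9.5 cap e at about 1 − 0.58 = 42%; the timing of the other outcomes is not given.

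**Step 4: the upper limit.** 1-sided 95% Clopper-Pearson limits, as an illustration, with 100 women, q = 50%, and only the late enrollees removed (90, 79 and 50 remain):

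| SABs | n = 100, as planned | n = 90 (s = 20%) | n = 79 (s = 43%) | n = 50 (s = 100%) |
|---|---|---|---|---|
| 0 | 2.95% | 3.27% | 3.72% | 5.82% |
| 2 | 6.16% | 6.83% | 7.76% | 12.06% |

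**Step 5: a different benchmark, risk per exposed pregnancy.** Let f be the share of exposed pregnancies that end before they would be individually enrolled. Those losses are retrospective and drop out, which raises the proportion among individual enrollees. If the remaining individual enrollees join before the window opens, the factor is

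1 − s + s(1 − q)/(1 − f),

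which is below 1 only if q > f. At s = 43% and q = 10%, f = 10% gives 1.00 and f = 20% gives 0.571 + 0.429 × 0.9/0.8 = 1.05. At q = 50% and f = 20% it is 0.571 + 0.429 × 0.5/0.8 = 0.84.

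**The case against.** - **Direction.** A reader might infer that the figure is biased low under any reading. The documents do not support that. Step 5 shows that against risk per exposed pregnancy, the exclusion of earlier losses can offset or outweigh late entry. On that benchmark, counting pregnancies that ended before the second trimester is also legitimate. Section 9.9 adds that high-risk or low-risk pregnancies may be preferentially reported. The downward direction is structural only against pregnancies ongoing and observable in the second trimester.
- **Contradiction.** A reader might infer that 9.7 simply overrides 8.0. It does not: 8.0 rejects an overall SAB rate, while 9.7 plans a narrower one. The narrowing answers the point about unrecognised early loss. It also answers late entry for women who enrol before the second trimester. Entry after that remains unanswered, including the week-16 example if dated from LMP.
- **Mitigation.** Section 9.7.3 names gestational age at enrolment as a possible subgroup, which could reveal the effect. It is optional and leaves the denominator unchanged. A SAP might add more, but the protocol itself fixes this denominator.
- **Missed signals.** A reader might infer that a safety signal would be lost. That goes too far. Section 11.0 lists SAB among the actively solicited SAEs and sends reported events to the sponsor's safety department within 1 business day. Section 9.7 also has retrospective fetal losses reviewed.
- **Size.** The largest figures need s = 100%, which departs from the external reports expected in 9.5. At s = 20% the late-enrollee factor is 0.90 to 0.98 over the range shown.

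**Conclusion.** The concern holds in a limited form. As an estimate of risk among pregnancies ongoing and under observation in the second trimester, the planned proportion and its upper limit are too low whenever late individual enrollees or earlier-ended pregnancies are included. Against risk per exposed pregnancy, the net direction cannot be stated.

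The size is unknown because the protocol gives no enrolment-time distribution. Over the assumed ranges, the late-enrollee factor runs from 0.98 (s = 20%, q = 10%) to 0.79 (s = 43%, q = 50%), and to 0.50 if every report is individual. It moves toward 1 as complete-capture reports make up more of the total.

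Severity is minor. The outcome is not among the three primary outcomes and has no comparator or decision rule, the registry is described as primarily descriptive, and individual SABs are captured separately.

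**What to change.** In Section 9.7, restrict the denominator to pregnancies ongoing at the start of the second trimester and under observation before week 20. These are individual reports enrolled before week 20 and ongoing at that start, plus complete-capture network/HMO reports ongoing at that start. Ideally, count time at risk from the later of that start and enrolment, so that part-window observation is also handled. State whether week 14 runs from LMP or from conception, since 9.4.1 allows both and the restricted denominator depends on it. In Section 8.0, state that this restricted figure is the only SAB estimate.

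If events prove very few, a simpler alternative is to report only the count of second-trimester SABs, with gestational age at enrolment and at loss, and no proportion.

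The change is wording in 8.0 and 9.7, plus the dating line in 9.4.1. No new data are needed: "Date the pregnancy exposure is registered" is already a minimum criterion in 9.2.3, and LMP, EDD and outcome date are collected under 9.4. The price is a smaller denominator and a wider interval; the count-only alternative gives up a rate.
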